6.6. Addressing recruitment challenges

We have given careful consideration to recruitment and adopted what we believe to be realistic estimates of the number/proportions of children: presenting with AOM; invited; assessed for eligibility and agreeing to participate. Recruitment will be difficult, with key challenges including: (i) relative infrequency AOM presentations; (ii) clinician equipoise and remembering to invite participation; (iii) the relatively short time available for the parent participation decision; and (iv) the short amount of time within primary care consultations to recruit.

The first and fourth challenges means that, unlike more prevalent conditions where sites can set aside staff and appointment time, CEDAR recruitment and randomisation will be conducted within consultations. We will collect only essential data, use 'easy to follow' parent instructions and same-day contact from the study team to address parents' questions. We have experience of designing such processes, as illustrated by the successful TARGET Cohort Study which recruited 8413 children from primary care.

The second challenge will be addressed through the use of clinician training in National Institute for Health and Care Excellence (NICE) guidelines and provision of systematic review evidence showing that a 'no' or 'delayed' antibiotic prescribing strategy is safe and effective for CEDAR children and the unproven value of anaesthetic drops. Clinicians will be offered paper and electronic ('pop ups' that respond to free-text (e.g. ear pain) or Read code (e.g. otalgia/otitis media) entry) CEDAR reminders. They will also be offered regular newsletters, recruitment activity tables and entry to a system of 'mini prizes' to acknowledge site recruitment contributions (e.g. site's first, fifth and tenth children; overall trial recruitment of 25th, 50th, 75th and 100th etc children). The web-based data collection system will facilitate real-time recruitment monitoring.

The third (and second) challenge will be mitigated by providing sites with letters and Parent Information Sheets that can be sent to registered families at the start of the winter season (if the GP practice agrees to participate in this optional activity) so that parents can make a participation 'decision-in-principle' before their child become unwell.

6.7. Maximising external validity

External validity is a challenge for the CEDAR trial as much as it is for other trials in general, and trials of acute otitis media (AOM) in particular. Indeed, a previous report has estimated that 44% of eligible children with AOM have been recruited to previous RCTs of antibiotics.¹

Three of the above recruitment assumptions will be key to the trial's external validity: (i) the proportion of presenting children invited to participate (this proportion will be monitored by asking sites to use standard diagnostic Read codes (e.g. otalgia and acute otitis media) allowing the study team to estimate presentation rates); (ii) the proportion meeting eligibility criteria (this proportion will be monitored through clinician completed screening logs); and (iii) the proportion of invited children agreeing to participate (this proportion will be monitored through clinician completed screening logs). We propose to carefully record as much information about children as possible in each of these three steps in order to: (i) rectify emerging problems (to maximise external validity) and (ii) measure (so we can report) the extent of the threat to external validity.

Furthermore, we will undertake a parallel observational cohort study to the degree to which children recruited to the CEDAR RCT are representative of the population of potentially eligible children.

6.8. Selection of recruiting sites

Primary care: GP practices; Walk-in and Out of Hours Centres; and Children's Emergency Departments. A webbased data collection platform will mean no geographical restriction to site participation.

We will recruit children whose parents are seeking medical advice for their child's ear pain or suspected AOM in a primary care setting. Organisations will include GP practices, Walk-in and Out of Hours Centres, and Children's Emergency Departments (CEDs) where first-point-of-contact care is provided by GPs, Nurse Practitioners (NPs) and CED doctors and nurses. Through the NIHR Primary Care Clinical Research Network, we have an established and highly functional working relationship with primary care sites across SW England and Wales. For example, the recent successfully completed HTA funded Diagnosis of Urinary Tract infection in Young children (DUTY) study coled by Professors [name] and [name] in Cardiff worked with 273 CED and practice nurses, 182 GPs and CED doctors, and 61 research nurses at 233 primary care sites to recruit 7,374 children. This study recruited from four Centres, three of which were the same Centres contributing to the CEDAR trial.

Using recent (post pneumococcal vaccine) RCGP seasonally adjusted AOM incidence data,² we estimate that each active GP site (based on average list 6500)³ will recruit between 0.5 and 1.3 children/month (assumes: 20% of presenting children have eligibility check; 66% eligible; and 25% agree to be randomised). Based on our previous experience of opportunistic recruitment to primary care trials, we estimate that the number of active primary care sites required to recruit 501 children to each of the RCT and OCS in 24 months will be in the region of 70-100.

6.9. Piloting recruitment

During the trial set-up stage, the trial procedures will be piloted through an iterative process where the study team will liaise closely with a number of independent primary care clinicians (to be identified through the CRN) to conduct detailed reviews of the data collection forms and procedures, and to discuss potential challenges to trial recruitment. Recruitment will be initiated in a small number of selected sites who will conduct internal piloting, i.e. establishing the efficacy of the planned recruitment procedures and materials with real patients. Due to a delay in the manufacture of the placebo, the internal pilot period will be initiated as a 2 arm pilot for the first 3 months, with the placebo arm being introduced as soon as possible. At the end of the internal pilot phase a detailed report will be sent to the funder to assess recruitment progress, assess the quality of our initial assumptions and identify any changes to recruitment strategy necessary to meet the target.

The data collected for children recruited during the internal pilot phase will be included in the trial dataset. A decision will be made as to whether to include the data for children recruited to the 2 arm pilot (for the first 3 months) will be made by the independent Trial Steering Committee based on a review of these data. Once recruitment has been proven to be effective and feasible within the initial 'piloting' sites, the placebo arm has been introduced, and any changes made in response to issues identified during this initial stage, the trial will be opened up to a wider range of participating sites.

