7.4. Dosing regimen

According to the randomisation schedule for the full trial, a child participating in the RCT will receive either active ear drops, placebo ear drops or no drops (children participating in the initial 2 arm pilot will receive either active ear drops or no ear drops). Children participating in the OCS will not receive any ear drops.

For children allocated to either of the two treatment arms within the RCT (active ear drops plus usual care, or placebo ear drops plus usual care), the allocation will be unknown to the clinician, parent, child and to the research team (with the exception of the Trial Pharmacist at UH Bristol Pharmacy). For children recruited during the 2 arm pilot, allocation to active ear drops will be known at the point of recruitment, following the assessment of eligibility and informed consent processes.

Regardless of allocation, parents in the two treatment arms will be asked to administer the ear drops no more than every 2 hours and a maximum of 12 times daily, in one or both ears to a maximum age-specific dosage per child, until pain is relieved, and for a maximum of 8 days. Missed doses should not be compensated for by giving a larger dose or more frequent doses. Clear dosage instructions will be provided on the medicine bottle and in the trial instructions for parents on how to give ear drops.

We anticipate that for 50% of children the duration of treatment until pain relieved will be 3 days, and that 90% of children's symptoms will have resolved by 8 days¹⁷.

There are no special dietary or other requirements to be imposed.

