The pain the child suffers is an important outcome for parents and will be a key secondary outcome, comparing whether the active drops are more effective than placebo drops. We will measure pain using the validated zero to 10 numerical rating scale we used in our previous RCT of delayed vs. same day antibiotic for childhood AOM.⁶ This trial showed mean pain scores of around 6.5 (same day antibiotics) and 5.5 (delayed) at 24 hours and overall mean pain scores of 2.6 (same day) and 3.6 (delayed). Regarding the minimum clinically important difference, our PPI group indicated that they would find a 10% (or greater) reduction in pain useful, and the largest difference observed in our previous trial using the same Symptom and Recovery Questionnaire was one point [[name] BMJ 2001]. Again assuming 90% power and α =0.05 we can detect a mean difference of 1 (SD=2.5 based on trial data) in pain score between the active and placebo ear drop groups, with 133 children per arm. Assuming 20% attrition and equal numbers in the three groups, we need 167 children per arm of the trial (more than for the primary outcome) and therefore 501 children in total.

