12.2. Sampling

Trial

Children will be recruited from primary care where the vast majority of children are managed. Selection bias will be minimised by encouraging recruiting sites to invite consecutive eligible patients and measured by asking them to record the characteristics of patients/reasons where this is not possible. Children not eligible for the trial or whose parents decline participation in the RCT will be invited to participate in the OCS.

Previous studies suggest 80-90% of children with AOM use antibiotics. The primary outcome of the study is to reduce antibiotic use in this group to 60-70%. Assuming 90% power and alpha set at 0.05 between 109 and 121 children would be needed in each of the active ear-drop and no-drop groups to detect a 20% reduction. As a key secondary outcome we are also interested in measuring whether the active eardrops reduce pain compared to the non-active ear-drops. Again using 90% power and alpha set at 0.05 a difference of 1.0 on the pain numerical rating scale (using an SD of 2.5 from our previous RCT suggests we need 133 children in each of the active and placebo ear drop groups. Thus using this slightly larger number of 133 children for all three groups and assuming no more than 20% attrition, we need to recruit 167 children per arm of the trial or 501 children in total.

A decision will taken as to whether children recruited during the initial 2 arm pilot (for the first 3 months, prior to the introduction of the delayed placebo) can be included in the analysis of the full 3 arm trial, following a review and comparison of the data collected under the two different randomisation schedules.

Observational cohort study

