12.3. Randomisation

Blinding of participants

The participants will be blinded to the trial in that only one third will be aware that they are in the usual care group. We will present this arm of the trial to parents as "one of the three treatment paths within the trial to which children will be randomised", rather than as "the control arm".

During the initial 2 arm pilot period, parents and clinicians will be aware that treatment allocation is either to the active treatment arm (active ear drops and usual care) or to the usual care/no ear drops ("control") arm.

Blinding of recruiting clinicians

The randomisation process will ensure that that there is no opportunity for clinicians to influence which child is allocated to which treatment. Clinicians recruiting children to the trial will be blinded until after treatment allocation. Once written informed consent has been obtained, the parent will be given a Patient Pack which will be identical across all three arms. Once the pack is opened during the consultation, the clinician and parent will learn whether or not the child has been allocated to one of the ear drop arms – but will remain blinded to allocation between the active and placebo drops.

For children recruited within the initial 2 arm pilot period, allocation to the active treatment arm (active ear drops and usual care) or to the "control" arm (usual care/no drops) will be known by the clinician and parent at the point of recruitment, following the eligibility assessment and informed consent processes.

Stratification

We will stratify by centre so that the distribution of the three arms are fairly equal between Bristol, Cardiff and Southampton. We will use sites' proven record of recruitment to previous studies to inform the distribution of recruitment packs at start-up.

Block size

We will randomise in batches of 30 within which treatment allocation will be equal (10:10:10) (for the initial 2 arm pilot, treatment allocation will also be equal (10:10)). We will closely monitor the recruitment at each centre, and adjust the ratio of the number of blocks provided to primary care sites within each trial centre to ensure they receive patient and medicine packs in proportion to their rate of recruitment.

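### Whether the open-label 2-arm pilot children enter the 3-arm analysis is to be decided after their data are reviewed, and nothing keeps them out of the blinded active v placebo pain comparison

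*Protocol*

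**What the plan says.** Section 6.9 first makes a general statement: "The data collected for children recruited during the internal pilot phase will be included in the trial dataset". It then makes an exception of the first three months. The decision on the 2-arm pilot children "will be made by the independent Trial Steering Committee based on a review of these data". Section 12.2 returns to the point: whether these children can be included in the analysis of the full 3-arm trial will be decided "following a review and comparison of the data collected under the two different randomisation schedules".

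The pilot differs from the main trial in two ways:

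- **Arms.** Section 7.4 says "children participating in the initial 2 arm pilot will receive either active ear drops or no ear drops", so there is no placebo. Section 12.3 makes the pilot allocation equal, in blocks of 10:10, against 10:10:10 later.
- **Blinding.** Section 7.4 says "For children recruited during the 2 arm pilot, allocation to active ear drops will be known at the point of recruitment". Section 12.3 agrees: in the pilot, "parents and clinicians will be aware that treatment allocation is either to the active treatment arm" or to usual care. In the 3-arm phase, families given drops do not know which drops they have.

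The key secondary analysis (section 12.5) compares parent-scored pain between active and placebo by linear regression, adjusting for baseline pain and centre. Appendix 9 says the effect on pain, being subjective, calls for a blinded design. On numbers, section 12.1 concludes "we need 167 children per arm of the trial (more than for the primary outcome) and therefore 501 children in total".

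**The concern.** Two things are wrong with the rule as written.

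First, an analysis set should be fixed before anyone sees the data that fill it. Here it is fixed afterwards. The comparison described in section 12.2 cannot be made until 3-arm data exist, so the choice falls within the main phase. The pilot data are open label, so a review that includes outcomes would show results by arm.

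Second, inclusion is not limited by comparison. If pilot active children joined the active v placebo pain analysis, three things would differ between the groups besides the drug:

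- **Expectation.** Pilot parents know the drops are active, and the same parents score the pain.
- **Site.** The pilot runs in a small set of selected sites, which move to three arms on a rolling basis (sections 6.9 and 9.6).
- **Calendar time.** No placebo child is recruited in the pilot period, and presentation of the illness is seasonal (section 6.5).

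The planned pain model has no term for schedule or period to absorb these differences. The comparison matters: under section 4.3 (c), a pain benefit over placebo would by itself lead to a recommendation of active drops.

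**Working it through.** **1. The plan's own figure.** Inputs from section 12.1: difference 1.0, SD 2.5, alpha 0.05 (taken as two-sided), power 90%, attrition 20%.

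- n per arm = 2 × 2.5² × (1.960 + 1.282)² / 1.0² = 131.3, or 132; the t-test version gives 132.3, or 133.
- 133 / 0.8 = 166.25, or 167; 3 × 167 = 501.

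The stated sizes reproduce. The fault is in the design rule, not the arithmetic.

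**2. Assumptions for the pain comparison.** The protocol gives neither the pilot size nor the effect of knowing that the drops are active.

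- Pilot size m = 20 or 40 children in total, half of them active.
- Open-label effect b = 0.5 or 1.0 point lower parent-scored pain.
- No true drug effect, and the pilot counted within 501.

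Formulas:

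- Placebo children = (501 − m)/3; active children = (501 − m)/3 + m/2; evaluable = 80% of each.
- Bias = b × (m/2) / active children.
- SE = 2.5 × √(1/evaluable active + 1/evaluable placebo).
- With d = bias/SE, two-sided type I error = 1 − Φ(1.96 − d) + Φ(−1.96 − d).

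| m | Active / placebo recruited | Active / placebo evaluable | Pilot share of active arm | SE | Bias, b = 0.5 | Type I error | Bias, b = 1.0 | Type I error |
|---|---|---|---|---|---|---|---|---|
| 20 | 170.3 / 160.3 | 136.3 / 128.3 | 5.9% | 0.308 | 0.03 | 5.1% | 0.06 | 5.4% |
| 40 | 173.7 / 153.7 | 138.9 / 122.9 | 11.5% | 0.310 | 0.06 | 5.4% | 0.12 | 6.6% |

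If the pilot came on top of 501, the shares would be 10/177 = 5.6% and 20/187 = 10.7%, which changes little. A larger pilot does more harm. With 63 children (501 × 3/24, a constant rate over the 24 months in section 6.8) and b = 1.0, the same formulas give a bias of 0.18 and type I error of 8.8%.

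**3. The primary comparison.** Simulation, 400,000 runs: 133 per arm in total, 80% consuming antibiotics in both arms, pilot included only when its own result favours active drops.

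| Pilot children per arm | False positives favouring active (nominal 2.5%) | Two-sided error |
|---|---|---|
| 10 | 3.2% | 5.2% |
| 20 | 3.4% | 5.2% |
| 40 | 3.7% | 5.2% |

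Taking the better of the two results each time gives 3.2 to 3.8% in favour of active drops.

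**4. Power for pain from concurrent children only.** Power = Φ(1/(2.5 × √(2/n)) − 1.96), with n the evaluable children per arm in the 3-arm phase.

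- No pilot within 501, n = 133: 90.4%.
- m = 20, n = 128.3: 89.3%.
- m = 40, n = 122.9: 88.0%.

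These losses arise only if the pilot counts within 501 and attrition reaches 20%. At 10% attrition, n is 144.3 and 138.3, and power is 92% and 91%.

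**The case against.** The best defence is that nothing bad is promised. Section 12.2 asks only whether the pilot children can be included, and that may be meant as a check of compatibility. The data to be reviewed are not said to be outcomes by arm. The decision lies with a committee described as independent, and that committee will also review an analysis plan that could settle the matter.

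Most of this is fair, and it limits the point. It does not remove it, because the protocol does more than stay silent: it states that the data will drive the choice and sets no bounds. Independence helps only in part. Appendix 3 lists the chief investigator and one or two other investigators in the committee's membership, while Appendix 6 reserves unblinded comparative data to the Data Monitoring Committee. A steering committee review of pilot outcomes by arm would sit badly with that.

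Four stronger readings are tempting, and the protocol does not support them:

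- **That pilot children will be pooled into the pain analysis.** Pooling is possible, not committed.
- **That the placebo arm exists only for blinding.** Section 4.3 also cites the soothing effect of the liquid and the placebo's effect on antibiotic use.
- **That placebo cannot reach 167 and power is lost.** This needs 501 to be a ceiling that includes the pilot. The synopsis has recruitment continue until the sample size is achieved, and Appendix 10 until the required follow-up datasets are in. Sections 6.5 and Appendix 4 also treat 20% attrition as conservative.
- **That error in the primary is uncontrolled.** That comparison is open by design and has concurrent 1:1 controls in the pilot. Two-sided error stays near 5%.

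A pilot of 63 is also hard to square with a small number of selected sites. At the 0.5 to 1.3 children per site per month in section 6.8, it would need about 16 to 42 practices over three months. For that reason 20 to 40 is used as the main range.

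**Conclusion.** The point holds as a fault in a stated rule. Sections 6.9 and 12.2 make inclusion of the 2-arm pilot children depend on a review of the data, with no criterion, no bar on outcomes by arm and no limit by comparison. Unblinded active children with no concurrent placebo controls could therefore enter the key secondary pain comparison.

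If they did, the bias would plausibly favour active drops. It would be about 0.03 to 0.12 points against a target difference of 1.0, with two-sided type I error of about 5.1 to 6.6%. These figures rest on the assumed 20 to 40 pilot children and open-label effect of 0.5 to 1.0 point, and they count expectation alone, not site or season. For the primary, the harm is about 3 to 4% one-sided error against 2.5%, and only if inclusion is chosen on the result.

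The numerical damage is modest at these sizes. The reason to act is that any later choice would be open to challenge, and the remedy is credible only before pilot outcomes are known.

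**What to change.** Amend sections 6.9 and 12.2 before any pilot outcomes are seen:

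- **Placebo comparisons.** Every comparison involving placebo uses only children randomised under the 3-arm schedule.
- **Primary comparison.** State by rule whether pilot children enter active v no drops. Either answer can be defended: the pilot has concurrent controls, but its parents know the drops are active and main-trial parents do not. If pilot children enter, add a schedule term (2-arm or 3-arm) and a sensitivity analysis without them.
- **Committee review.** Limit the Trial Steering Committee's review of the pilot to conduct and data quality, without outcomes by arm.
- **Sample size.** State whether pilot children count within the 501. If they do, restate the power for pain on the concurrent active and placebo numbers: about 88 to 89% for 20 to 40 pilot children at 20% attrition.

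The general statement in section 6.9 that internal pilot data are included should be reworded to match. The cost is one protocol paragraph, one model term if the pilot is included, and possibly a slightly lower stated power for pain. No extra patients are needed.

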6.10. Database search

During the internal pilot phase, participating GP practices will be asked to conduct a monthly database search of children presenting with AOM (using the following read codes: F527, acute right otitis media; F526, acute left otitis media; and F528, acute bilateral otitis media) in order to enable the study team to assess the proportion of presenting children who are invited to participate. (We have assumed this will be 0.2, since many children will present to primary care sites at inconvenient times, e.g. insufficient recruiting staff capacity).

